N-of-1 trials are single patient randomized controlled trials (RCTs) that systematically compare various therapeutic options in the patient in a crossover fashion, applying techniques borrowed from traditional trials to minimize confounding and bias. The results are used to inform treatment decisions for the individual patient and in some circumstances can also be aggregated across participants to produce population-level estimates. Although n-of-1 trials were first proposed decades ago, their potential value is now being more widely recognized. However it is unclear whether their potential benefits would justify the effort required to use them in clinical practice. We propose a series of n-of-1 trials in hypertensive children with CKD and ESRD to determine if ambulatory BP control is improved after the antihypertensive regimen is modified based on the results of an n-of-1 trial.

With KL-2 funding we previously conducted a series of n-of-1 trials with repeated ambulatory BP monitoring (ABPM) in 42 children with primary HTN, and found them to be useful to differentiate drug response. In that study, n-of-1 trials were designed to identify which of three commonly used medications (amlodipine, hydrochlorothiazide (HCTZ), and lisinopril) when prescribed as monotherapy produced the greatest ambulatory BP reduction for the individual patient without unacceptable side effects. This study, HSC-MS-13-0287: "Individualizing the treatment of essential hypertension in adolescents using n-of-1 trials", was determined to be a QI activity by the UTH IRB. We recruited patients from our pediatric hypertension clinic from June 2013 to July 2016. Among 55 patients meeting inclusion criteria, 42 (76%) agreed to participate in an n-of-1 trial with little urging. In this sample (N=42) no single drug emerged as the preferred therapy for the majority of patients, with amlodipine selected for 19%, lisinopril 38%, HCTZ 10%. The n-of-1 trial resulted in drug discontinuation in 17% and BP remained uncontrolled on a single drug in 10%.

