The overarching goal of this proposal, which addresses key knowledge gaps in the management of hypertension in pediatric kidney disease and in the design and conduct of n-of-1 trials, is to develop a deeper understanding of the feasibility and generalizability of n-of-1 trials to children with kidney disease. If we find that BP control is improved when the drug regimen is modified based on an n-of-1 trial, this approach should be tested more rigorously in a multicenter RCT. Our next step also may include the development of a decision support tool informed by the results of previous n-of-1 trials to provide Bayesian probabilities of treatment success with various treatment strategies based on patient characteristics. If shown to improve the management of HTN in patients with CKD/ESRD, this could result in improved long-term BP control and intermediate CV outcomes, and holds potential to slow the progression of renal disease in children.

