#### N-of-1 trial protocol:

The n-of-1 trial will be customized for the individual patient to test which treatment strategy produces superior BP reduction without unacceptable side effects. After discussion with the patient/caregiver to identify whether they have specific concerns about particular medications, the nephrologist will decide which two drugs and dosages will be tested in the n-of-1 trial. Drugs from the  $\alpha$ -blocker and  $\beta$ -blocker drug classes will not be eligible for testing due to the risk of withdrawal syndrome associated with abrupt cessation. These and all other previously prescribed antihypertensive drugs not being tested will be continued at unchanged doses during the n-of-1 trial.

The two drugs will be assessed at clinician-selected dosing in a randomized treatment order (ex ABAB), for two weeks per treatment period and two treatment periods per drug with increasing doses assessed for additional treatment periods if BP remains elevated with initial dosing of both regimens. Treatment response for each regimen will be measured with a side effect survey administered to patient and caretaker and 24-hour ABPM (Spacelabs) on day 14 of each 2-week treatment period. ABPM readings every 20 min for

24 hours. For patients unwilling or unable to undergo repeated ABPM, home BP monitoring (Qardioarm) will be used, (mean of 3 readings, 1 minute apart) twice daily on days 13 and 14 of each 2-week treatment period.

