Blinding can be employed in n-of-1 trials to minimize biased assessments of treatment effects. In our past studies, we have not made any attempt to mask patients/caregivers to the current treatment. In the present study, we will offer blinding to each patient/caregiver to assess the acceptability of blinding. If the family declines blinding, then the reasons will be recorded. If they agree to be blinded, patients will be advised to fill both prescriptions at the start of the trial. Medication will be dispensed by the patient's usual retail pharmacy with costs covered through usual insurance coverage. Caregivers who opt in to blinding will provide the research team with the dispensed medications, who will sort out the pills into a 31 day pill organizer according to the randomized treatment order and refill as needed once monthly. While a patient could theoretically decipher their treatment based on pill appearance, those who opt in to blinding are less likely to attempt to unblind themselves. Additionally, costly pharmacy fees would make other blinding approaches less feasible within the funding limitations of the current pilot award.

At the conclusion of all treatment periods, the clinician will review the BP and side effect survey findings with the family via either an in person or telemedicine visit. When the patient, caregiver, and clinician jointly conclude that there is a sufficiently high probability that the preferred treatment has been identified (defined as that which produces superior BP reduction without unacceptable side effects), it will be prescribed for long-term use along with all other previously prescribed antihypertensive medications, and the n-of-1 trial will conclude.

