Analytic approach: The primary outcome of 24-hr MAP will be analyzed by generalized linear mixed model (GLMM) accounting for repeated ABPMs over the study period including the pre-n-of-1 ABPM assessment. The mixed model will contain a random intercept for each patient and appropriate link function based on the distribution of the 24-hr mean MAP. From this model, we will report the average difference between 24-hr MAP at 6 months and baseline ABPM. Success for the n-of-1 trial will be defined as any decrease in mean 24-hr MAP at 6 months compared to pre-n-of-1 ABPM. Bayesian models with uninformative, neutral priors for regression coefficients and error variances will be used to determine the probability of decrease in 24-hr MAP after the n-of-1 trial. All analyses will be conducted on an intention-to-treat basis with the GLMM allowing inclusion of patients with missing BP measurements at some time points. Secondary binary outcome of 24-hr MAP to <50th %ile will be similarly analyzed over the study period to determine if the proportion of patients with 24-hr MAP to <50th %ile is greater after the n-of-1 trial. If the sample size allows, exploratory analysis will examine strata specific effects for sex, age group, race, BMI, CKD stage, medication class, and number of anti-hypertensive medications.

**Aim 3: Describe treatment strategies in the management of hypertension in children with chronic kidney disease at major pediatric centers nationally (retrospective cohort study of de-identified multicenter dataset that does not include patients from our institution).**

Our current and previous n-of-1 trial protocols were designed based on our local prescribing preferences in HTN management. As we prepare to design a future multicenter RCT, it will be essential to better understand national prescribing patterns to inform the design of n-of-1 trial protocols that are generalizable and broadly appealing to pediatric nephrologists at other centers. Previous large studies describing antihypertensive medication prescribing patterns in childhood kidney disease have been limited to cross-sectional design, but the proposed observational study would allow longitudinal descriptions of treatment patterns within an individual over time.

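### The Aim 2 success rule credits any 6-month fall in MAP to the n-of-1 trial, but the contrast is an uncontrolled before-after change that includes dose and drug changes

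*Combined protocol and SAP*

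**What the plan says.** Aim 2 takes the change in 24-hr MAP from an enrolment ABPM to a 6-month ABPM as its primary outcome, and about 20 patients are expected. The analytic approach fits a mixed model with a random intercept per patient, reports the average 6-month difference from baseline, and then states: "Success for the n-of-1 trial will be defined as any decrease in mean 24-hr MAP at 6 months". Bayesian models with neutral priors "will be used to determine the probability of decrease in 24-hr MAP after the n-of-1 trial"; no cut-off is given for that probability. The text does not say outright whether success is judged for each patient or for the group.

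The section on the n-of-1 trial protocol describes what lies between the two ABPMs:

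- The nephrologist picks two drugs and their doses for each patient, and they are given in randomised order over two 2-week periods each.
- The protocol allows "increasing doses assessed for additional treatment periods if BP remains elevated with initial dosing of both regimens".
- When family and clinician agree that "there is a sufficiently high probability that the preferred treatment has been identified", "it will be prescribed for long-term use along with all other previously prescribed antihypertensive medications".
- The final ABPM is fixed at 6 months whenever the n-of-1 trial ended, on the regimen then in use (Aim 2, Outcome measurement).

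The Specific Aims section says that if BP control is found to be improved "when the drug regimen is modified based on an n-of-1 trial, this approach should be tested more rigorously in a multicenter RCT".

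**The concern.** The rule names a cause, the n-of-1 trial, for a change that has no comparator. At least four things can move MAP between the two ABPMs: which drug was chosen, a higher dose, a different number of drugs, and anything else that changed over six months (adherence, for example). Only the first is what selection by n-of-1 trial adds. The rule also has no minimum size and no required level of certainty, so chance alone will often satisfy it.

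At stake is what the pilot may claim. An observed improvement is the stated reason for going on to a multicentre RCT. A fall produced by more intensive treatment would be recorded as success of the n-of-1 trial and would count towards that reason.

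**Working it through.** **The plan's own figures.** There is no power calculation to reproduce. Enrolment of 20 rests on the number of potentially eligible patients, which is not given, and on the previous acceptance rate. That rate reproduces: 42/55 = 76.4%. Enrolling 20 would then imply 20/0.764 ≈ 26 eligible patients.

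**Time available for other changes.** Four 2-week periods take 8 weeks. Taking 6 months as 26 weeks, up to about 18 weeks remain before the final ABPM.

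**Inputs for the rule.** N = 20 is the plan's figure. The following are assumptions:

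- within-patient SD of a 24-hr MAP, s = 4, 5 or 6 mmHg;
- share of patients intensified by 6 months, f = 0, 1/4 or 1/2;
- fall in MAP from intensification, e = 2 or 5 mmHg;
- no benefit from the choice of drug.

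As a simplification, only the baseline and 6-month ABPMs are used.

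**Group reading.** Let change be baseline minus 6 months. Its mean is m = e·f, and its variance per patient is v = 2s² + e²·f(1−f). Then P(any decrease) = Φ(m / √(v/20)).

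With f = 0, m = 0 and the probability is Φ(0) = 50%, whatever s and N are.

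Example with e = 5, f = 1/4, s = 5: m = 1.25; v = 50 + 25 × 0.1875 = 54.69; SE = √(54.69/20) = 1.654; Φ(0.756) = 77.5%.

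| e (mmHg) | f | s = 4 | s = 5 | s = 6 |
|---|---|---|---|---|
| 2 | 1/4 | 65.2% | 62.3% | 60.3% |
| 2 | 1/2 | 78.2% | 73.4% | 70.0% |
| 5 | 1/4 | 82.2% | 77.5% | 73.8% |
| 5 | 1/2 | 96.5% | 93.2% | 89.7% |

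**Per-patient reading.** The share of patients showing a fall is f·Φ(e/(s√2)) + 0.5(1−f). It is 50% with no change. At e = 5 it is 56-58% with a quarter intensified and 61-66% with half.

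**Allowing for reduced regimens.** In the earlier study in primary hypertension (Background), "The n-of-1 trial resulted in drug discontinuation in 17" percent of patients. Suppose that share, r = 0.17, is also reduced here and MAP rises by e in them. Then m = e(f−r) and v = 2s² + e²[(f+r) − (f−r)²]. For f = 1/4 and 1/2 the group results are:

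- e = 5: 58-61% and 79-86%;
- e = 2: 53-55% and 63-69%. For example, with f = 1/4 and s = 5, m = 0.16, v = 51.65, SE = 1.607 and Φ(0.100) = 54.0%.

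**What the Bayesian probability adds.** A flat-prior posterior was approximated by t with 19 df on the 20 paired changes (100,000 simulated trials, e = 5, illustrative cut-off 0.95). The share of trials above the cut-off is 5% with no change, 15-22% with a quarter intensified and 33-54% with half. With 17% also reduced, the last two become 7-8% and 19-28%. A cut-off therefore protects against chance but not against intensification, so the wording of the conclusion must change as well.

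**Expected precision.** With no regimen changes, the 95% half-width for the mean change is 2.093 × √(2s²/20): 2.093 × 1.265 = 2.6 mmHg at s = 4, and 2.093 × 1.897 = 4.0 mmHg at s = 6.

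**The case against.** The strongest reply is that the plan never says a fall will be credited to having chosen the better drug. Aim 2 asks only whether the regimen after the n-of-1 trial lowers BP more than the one before it. Dose increases are a step of the protocol itself and so belong to the strategy being studied. The study is called a pilot, and attribution is left to a later RCT. This largely stands, and it is why the 6-month contrast should be kept. What remains is the rule itself, which calls any fall, however small or uncertain, success of the n-of-1 trial.

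A second reply is that the size is assumed. That is so. A 2 mmHg effect gives much smaller figures than 5 mmHg. Eligibility does not depend on BP control, so well-controlled patients can enrol, and doses rise only if BP stays elevated; half the sample intensified is not shown to be likely. Nor do the documents say that BP rose in the patients who discontinued a drug. The 50% under no change needs none of these inputs.

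A reader might infer three stronger points that the documents do not support:

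- **That the randomised periods are wasted, or that a missing pooled comparison of drug A with drug B is an error.** The periods inform each patient's choice, and the nephrologist selects the pair for each patient, so A and B have no common meaning. The between-patient SD of the difference would mix drug-pair differences with variation in response. An F test of the patients' A−B differences on 20 and 40 df (s = 5) rejects 58.5% of the time under a constant 5 mmHg drug difference with no response variation, against 57% under a true response SD of 5 mmHg. It cannot tell the two apart.
- **That regression to the mean drives the result.** Patients are not selected on baseline BP, so the point does not rest on it.
- **That uncertainty is ignored.** The average difference and a posterior probability are both planned; they are just not tied to the success rule.

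**Conclusion.** The concern holds as a point about the success rule and its label. As written, the rule declares success half the time when nothing has changed. With no benefit from drug choice and a quarter to half of 20 patients intensified, it does so about 60-78% of the time at an assumed 2 mmHg effect, or 74-97% at 5 mmHg, for an assumed within-patient SD of 4-6 mmHg. Offsetting reductions lower these figures. The contrast supports a statement about new regimen against old, but not one about the success of n-of-1 selection. Severity is minor to moderate: the harm is confined to what the pilot claims and to the case it makes for the RCT, which can test attribution properly.

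**What to change.** Keep the 6-month contrast and the Bayesian model, and change four things:

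1. Replace the rule that any decrease is success with this description of the result: uncontrolled pre-post change under the n-of-1 strategy, including dose and drug changes.
2. State that it is judged at group level.
3. Base the conclusion on the mean change with its 95% interval and on the planned probability of decrease, with a cut-off for that probability fixed in advance.
4. Tabulate drug count and tested-drug dose at baseline and at 6 months, as description only. Splitting the MAP change by intensified, unchanged or reduced regimen would condition on something decided after baseline for clinical reasons, and it cannot restore attribution.

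Optional and exploratory: summarise each patient's difference between the two drugs over the randomised periods, with an interval, labelled by drug or class. Show patients followed by home monitoring separately ("For patients unwilling or unable to undergo repeated ABPM, home BP monitoring (Qardioarm) will be used"). Do not present a between-patient SD or a heterogeneity test as variation in response.

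The cost is revised analysis wording, two coded fields known from prescribing, and a narrower claim. No extra visits are needed.
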